5.1 Overall Design

The study is a Phase 2, double-blind, placebo-controlled study of sargramostim in the Alzheimer's disease population. It will include individuals diagnosed with mild AD or moderate AD (or meeting criteria consistent with a provisional research diagnosis), consistent with MoCA score range of 4-24 (137, 138,139) at time of screening and NIA-AA (2018) research criteria. The study includes a screening period of up to 12-weeks, a treatment period of 24-weeks, and an approximately 6-week follow-up. Individuals who meet inclusion/exclusion criteria will be randomized in a double-blind manner, in an approximate 2:1 randomization ratio to one of the following treatments:

- Sargramostim 178.57 μg/m²/day subcutaneously (7 days per week) (This is adjustment from original 250 μg/m²/day subcutaneously (5 days per week). Any participant on the original dosing schedule will be changed to the new dosing schedule the first refill after amendment is approved)
- Placebo equivalent volume subcutaneously (7 days per week).

The estimated maximum main study visits for each individual participant is approximately 55, including 4 screening visits (Tier .5-3), 48 treatment period visits (i.e. 4 in-person clinic visits, 20 at home visits, and 24 weekly blood draw at central laboratory for 2nd safety CBC w/diff), 1 End of Treatment visit, 1 FDG PET visit, and 1 visit in the post-treatment follow-up phase. Participants who opt to participate in the optional PET substudy or optional LP substudy would have 2 additional visits, 1 during screening, and 1 during either EOT (LP) or follow-up (PET). All participants will have the option of visits to happen at the main study site when the home nursing visit option is available.

5.1.1 Investigational Product:

Recombinant human GM-CSF is commercially available from Partner Therapeutics as Leukine[®]/sargramostim, which is FDA-approved for use in elderly patients (> 55 years old) and has a long and well documented safety record. The investigational product will be obtained by the study Sponsor for use in this clinical trial, and prepared by an unblinded pharmacist for administration to the randomized participant.

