- Diagnostic assessment for mild-to-moderate Alzheimer's disease: In the case of a potential participant who otherwise meets criteria for inclusion in the study, has a confirmed diagnosis of mild cognitive impairment, but does not have a confirmed diagnosis of mild or moderate AD, the PI or sub-I may conduct an evaluation as part of screening utilizing clinical interview and validated measures of functioning related to disease severity (such as the Functional Ability Questionnaire (FAQ) and/or the Dementia Severity Rating Scale (DSRS) to create a research provisional diagnosis of mild or moderate AD. NOTE: The PI or sub-I who conducts the

diagnostic assessment will meet with at least one additional study doctor or qualified sub-Investigator to arrive at consensus of the research provisional diagnosis.

- Safety evaluations (C-SSRS, GDS, GAD-7)
 - Columbia Suicide Severity Rating Scale (C-SSRS): The C-SSRS will be administered at the Screening Visit to assess psychological health. It was designed to capture the occurrence, severity and frequency of suicide related thoughts and behaviors during the defined assessment period. At screening, the C-SSRS version to be administered will be the "Baseline" version, with individuals who score at high risk for suicidality (positive response to items 4 and/or 5) will be excluded. If any results of the C-SSRS warrant concern for the participant's well-being, the participant will either be referred to their appropriate medical provider or if urgent, escorted or transferred to the UCH Emergency Department for follow-up care.
 - Geriatric Depression Scale (GDS): The GDS is a simple 30-item measure used to identify depression in elderly individuals. The simplicity of the GDS (questions are answered only by "yes" or "no") enables the scale to be used with ill or moderately cognitively impaired individuals. One point is assigned to each answer and the cumulative score is rated on a scoring grid. The grid sets a range of 0 to 9 as 'normal', 10 to 19 as 'mildly depressed', and 20 to 30 as 'severely depressed'.

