6.1 Inclusion and Exclusion Criteria

6.1.1 Inclusion Criteria

All participants must meet the following criteria to be included into the study:

Inclusion Criteria

Participant Characteristics

- 1 Males or females between age 60 and 85 years, inclusive, at time of consent.
- Have a dedicated partner/caregiver informant who is in the company of the participant at least 12 hours a week, who can accompany them to scheduled visits, and who is able to provide accurate reporting upon the behavioral, cognitive and functional abilities of the participant. Additionally, the study partner (or LAR or caregiver, if different) must be willing and able to administer the treatment injections. If a study partner must withdrawal from study participation, a replacement study partner may be allowed, at the investigators discretion. The replacement study partner, would need to agree to and sign a separate informed consent on the first visit that he/she accompanies the participant to participate.
- 3 Be physically able to participate by medical history, clinical exam, and other testing, with adequate visual acuity and auditory discrimination.
- Be willing / able to provide written informed consent or assent. If assent is provided, consent must be provided by a legally authorized representative (LAR) or proxy decision maker, who may or may not be the dedicated study partner / caregiver. Documentation of LAR or proxy decision maker status will follow local laws and regulations.

Note: Individuals utilizing a proxy decision maker will not be able to participate in optional sub-studies as a proxy decision maker cannot provide consent for optional non-therapeutic interventions.

Must reside within a proximity of the study site that will not preclude their regularly-scheduled participation in the trial, as well as a catchment area for local lab blood draws (i.e. central contracted laboratory).

Disease Characteristics

- Meet criteria for probable AD dementia according to the National Institute of Aging

 Alzheimer's Association (NIA-AA) 2018 core research criteria 109, and have the following at screening:
 - A diagnosis of mild AD or moderate AD, or
 - A provisional research diagnosis consistent with probable mild AD or moderate AD, and
 - MoCA score of 4-24 inclusive.
- Have positive biomarker for brain amyloid pathology as shown by:

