8.3.2 MRI

Atrophy in the entorhinal cortex (ERC), parahippocampal gyrus, and hippocampus (HPC), measured on MRI scans, predicts future cognitive decline and conversion among individuals with mild cognitive impairment (MCI) to AD ^{110, 111}. Severity of MTA, assessed with MRI scans, is strongly associated with

severity of medial temporal lobe degenerative pathology, especially the severity of neurofibrillary pathology, at autopsy ¹¹². Because of the high prevalence of AD in the elderly, 85–90% of all degenerative pathology in the medial temporal lobe, either alone or in combination with other diseases, is AD pathology ¹¹³.

An automated rating system to grade the severity of atrophy in the entire medial temporal region (MTA) will be employed using the FreeSurfer software automated rating system of individual medial temporal structures, i.e., the HPC, ERC, parahippocampal gyrus and perirhinal cortex (PRC), which are specific regions of interest (ROIs) in AD pathogenesis. It has been shown that these individual and summed MTA scores distinguish AD and acute MCI individuals from normal elderly control individuals and predict progression from acute MCI to dementia/AD ^{114, 115}.

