ApoE genotyping will be performed using blood samples collected on Day 1 of this trial for each participant. ApoE genotype will be determined either by Athena Diagnostics, or in the University of Colorado laboratory under the direction of [name], using established methods. Outcomes in the context of ApoE genotype will be compared. The genetic testing will be carried out at the end of the trial, and participants will not be notified of any genetic testing results.

To assess the effect of sargramostim treatment, as compared to placebo, on inhibiting MTA in individuals with mild-to-moderate AD.

MTA will be assessed using an automated rating system to grade the severity of atrophy in the entire medial temporal region will be employed using the FreeSurfer software automated rating system of individual medial temporal structures, i.e., the hippocampus (HPC), entorhinal cortex (ERC) and perirhinal cortex (PRC), which are specific regions of interest (ROIs) in AD pathogenesis. FreeSurfer automatically computes cortical reconstruction and volumetric segmentation, including segmentation of the subcortical white matter and deep gray matter volumetric structures ¹²⁸ and parcellation of the cortical surface ¹²⁹ according to a previously published parcellation scheme ¹³⁰. This labels cortical sulci and gyri, and thickness values are calculated in the ROIs.

Group comparisons of changes in regional volumes and thicknesses will be analyzed using a series of one-way analyses of variance (ANOVAs). The Scheffé post hoc procedure will be used to examine differences between means, and Pearson product—moment correlation coefficients will be used to evaluate the strength of relationships between changes in regional volumes and thicknesses and cognitive measures. Receiver operator curve analyses will determine sensitivity and specificity of various MTA cut-off points for distinguishing between diagnostic groups. Hazard ratios (HRs) for specific predictors of MTA progression and regression will be calculated using a three-state Markov model in continuous time. The proportional intensity model will be used to analyze effects of covariates on HRs.

To assess the effect of sargramostim treatment, as compared to placebo, on AD related changes in blood brain barrier permeability in individuals with mild-to-moderate AD.

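### Protocol 9.2.3 plans an ROC of MTA cut-offs between diagnostic groups that the trial neither enrols nor defines, and 8.3.2 and 9.2.3 list different FreeSurfer regions for MTA

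*Protocol*

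**What the plan says.** The MTA objective in Protocol section 9.2.3 is the effect of sargramostim against placebo in mild-to-moderate AD. The analysis paragraph compares the groups on change in regional volume and thickness by a series of one-way ANOVAs. It then adds: "Receiver operator curve analyses will determine sensitivity and specificity of various MTA cut-off points for distinguishing between diagnostic groups".

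On who is enrolled:
- Section 5.1: "It will include individuals diagnosed with mild AD or moderate AD (or meeting criteria consistent with a provisional research diagnosis".
- Section 6.1.1 requires participants to "Meet criteria for probable AD dementia according to the National Institute of Aging"–Alzheimer's Association framework, with "A diagnosis of mild AD or moderate AD, or" a provisional research diagnosis of the same.
- Section 5.3.1: someone who arrives with confirmed MCI but no confirmed AD diagnosis may be assessed by the study doctors "to create a research provisional diagnosis of mild or moderate AD".

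On the diagnostic use of MTA, section 8.3.2 cites earlier work showing that "these individual and summed MTA scores distinguish AD and acute MCI individuals from normal elderly control individuals".

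On the regions that the FreeSurfer rating covers:
- Section 8.3.2: "the HPC, ERC, parahippocampal gyrus and perirhinal cortex (PRC".
- Section 9.2.3: "the hippocampus (HPC), entorhinal cortex (ERC) and perirhinal cortex (PRC".

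**The concern.** An ROC analysis needs at least two groups whose true status is known. The only diagnostic groups that the protocol links to MTA are AD, MCI and normal elderly people, and the trial enrols the first alone. The sentence thus commits the trial to sensitivity and specificity estimates with no stated reference classification. Whatever split was chosen later, the result would not address the objective it stands under.

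The region lists raise a different problem. They specify the same automated rating, and each is introduced as a complete enumeration, so an analyst cannot follow both. If the choice is left until treatment codes are known, whether one region enters the set of tests could be settled with the data in view.

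**Working it through.** The plan gives no figure for either part, so the main check is a comparison of the text.

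**1. Which groups could the ROC separate?**

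| Candidate split | Available? | Why |
|---|---|---|
| AD, MCI, normal controls (8.3.2) | No | 6.1.1 requires probable AD dementia; no control or MCI group is enrolled |
| MCI entrants against the rest | No | Under 5.3.1 they enter only with a provisional diagnosis of mild or moderate AD |
| AD against another cognitive disorder | No | 6.1.2 excludes other conditions that can impair cognition |
| Sargramostim against placebo | Not a diagnosis | Arm is assigned at random |
| Mild against moderate AD | Yes, but not stated | 5.1 and 6.1.1 recognise both severities; 9.2.3 does not name them as the groups |

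Only the last row can be carried out as an analysis of diagnosis. It would describe severity, not a treatment effect.

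**2. Which regions?**

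| Region | 8.3.2 | 9.2.3 |
|---|---|---|
| Hippocampus | yes | yes |
| Entorhinal cortex | yes | yes |
| Perirhinal cortex | yes | yes |
| Parahippocampal gyrus | yes | no |
| Count | 4 | 3 |

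The lists share three regions and differ by one. On the stated plan, the effect is whether the parahippocampal gyrus is among the regions analysed.

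**3. The optional covariate.** The one-way ANOVA on change is valid in a randomised trial. To see what adjustment for the screening value could add, take N = 42 completers (28 and 14, section 9.1), equal variances at the two times, one normal covariate, and a screening-to-EOT correlation rho. The documents do not give rho, so it is assumed.

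Variance ratio, ANCOVA to change score = (1 + rho)/2 × (N − 3)/(N − 4) = (1 + rho)/2 × 39/38.

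- rho = 0.80: 0.900 × 39/38 = 0.924
- rho = 0.90: 0.950 × 39/38 = 0.975
- rho = 0.98: 0.990 × 39/38 = 1.016
- Break-even: rho = 2 × 38/39 − 1 = 0.949

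The variance falls by about 8% at 0.80 and 3% at 0.90, and rises slightly at 0.98. The 39/38 factor is the cost of estimating the slope when the arms differ by chance on the covariate. Error degrees of freedom go from 40 to 39.

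**The case against.** The strongest defence is that section 9.2.3 never offers the ROC as the test of treatment. The ANOVAs do that, and a supplementary descriptive analysis is not wrong because it leaves the arms uncompared; the planned correlations of regional change with cognition do not compare them either. Mild and moderate AD give a possible split, and section 9.3.1 defers the full plan to an SAP, which could name it. Both sections also give the whole medial temporal region as the target.

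Much of this stands. A reader might infer that the MTA objective has no valid treatment comparison; the ANOVAs show otherwise. What the defence does not remove is that the stated target is undefined, and that the contrast which the protocol itself associates with MTA cannot be supplied by an SAP for people who are not enrolled. A shared target region also does not reconcile two different complete lists.

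Other stronger readings are tempting but lack support:
- **A summed MTA score changes its meaning.** Summed scores appear in 8.3.2 only in a sentence about earlier literature. No analysis in 9.2.3 uses one.
- **The mismatch reaches the FDG-PET objective.** Sections 4.5 and 9.2.3 mention only a potential correlation with MTA change, not a committed analysis.
- **Section 4.5 gives a third region list.** It names the entorhinal cortex, parahippocampal gyrus and hippocampus in a rationale sentence, not in a specification of the measurement.
- **The Scheffé step is an error.** With two arms it is redundant, and removing it changes no result.
- **The precision of a mild-versus-moderate ROC can be quoted.** The split, the AUC and the choice of positive class would all have to be assumed.

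**Conclusion.** Both points hold as faults of wording. The ROC sentence names groups that the trial neither defines nor, in the sense used in section 8.3.2, enrols. The region lists in 8.3.2 and 9.2.3 conflict by one region, the parahippocampal gyrus.

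The size is minor. MTA is an exploratory objective, its treatment comparison remains in place, and neither the safety primary nor the MMSE secondary conclusion is touched. These conclusions rest on the text alone. Only the remark on covariate adjustment depends on an assumed correlation, and it is a possible refinement, not a correction.

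**What to change.** 1. In 9.2.3, delete the ROC sentence. Alternatively, relabel it as a descriptive analysis of mild against moderate AD and state that it is not a test of treatment.
2. Use one region list in 8.3.2 and 9.2.3, fixed before unblinding. The four-region list would serve: the rationale in 4.5 also names the parahippocampal gyrus, and no new scan is needed.
3. Optionally, analyse each regional volume or thickness by ANCOVA on arm with the screening value as covariate. The screening MRI is already collected. The cost is one degree of freedom, and the gain is small or nil if the screening-to-EOT correlation is very high.

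Items 1 and 2 are wording changes with no new data, visits or participants.

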9.3 Additional Statistical Consideration

Additional statistical tests that may be utilized include: independent t-tests to examine differences between means; the Chi-square test to assess association between variables; logistical regression to calculate the ratio of the odds of an event occurring in one group compared to another group, and longitudinal regression to analyze the data over time.

9.3.1 Full Statistical Analysis Plan

A full statistical analysis plan will be developed and approved prior to final database lock of participant data and will be outlined in a separate Statistical Analysis Plan (SAP) document.

9.4 Interim Analyses

No interim analyses will be conducted as a part of this trial.

9.5 Data Storage:

All data collected at the study site will be stored in REDCap, a HIPPA compliant database. Data collected will include general participant information (e.g., age, phone, address, etc.), background health information, and research outcomes. The Principal Investigator is responsible for the individually identifiable private health information. Access to the REDCap database key will be restricted to the research team approved on the application in order to minimize risk of unintentional disclosure. All affiliated/local principal investigators, co-investigators, and research coordinators involved in consenting and carrying out the proposed study will complete Collaborative Institutional Training Initiative, an online basic Course in Human Subject Protections, and the HIPAA research course prior to submitting a protocol. Source data will be collected and stored in participant binders, OnCore CTMS, Epic EMR, and the CU_AMC computer system.

For the general manipulation of data, the clinical data will be transformed into a de-identified data set using the unique study IDs. Any paper record of the data will be kept under lock and key with the Principal Investigator.

9.6 Specimen Storage:

Samples will be stored for at least 10 years, or the entire course of this study. Excess samples may also be added to the University of Colorado Alzheimer's and Cognition Center (CUACC) Biobank for future internal or external studies, if given consent by the participant. If a participant withdraws from the study, the samples will be discarded at the written request of the participant or appropriate consenting party.

9.7 Control of Conflict of Interest:

The Sponsor and Principal Investigator, [name], was one of the conceivers of the Arthritis/GM-CSF/G-CSF approach to AD therapy and is one of the inventors on several University of South Florida issued patents on the use of GM-CSF to improve cognition and/or to reduce amyloid deposition in AD and/or in chemobrain. These patents have never been licensed and are of no commercial value presently. To eliminate any real or even perceived conflict of interest, [name] has relinquished any and all personal rights to shared royalties from USF patents and has instructed the USF Technology Transfer Office to transfer any such income that might come in the future to the University of Colorado Foundation to support research by the [name] Alzheimer Dementia Fund. Furthermore, the following steps will be used to help further isolate [name] from potential influence related to the outcomes of the trial and to ensure that the trial is carried out with the highest level of scientific integrity:

1) All investigators who interact with participants directly and all investigators who collect and record data will have zero financial interest in the outcome of the study and will be blinded to the treatment group.

- 2) Endpoints are quantitative and objective (i.e., assessments of cognition using a battery of neuropsychological and clinical assessments used in the UCH clinic, brain imaging, and measures of blood biomarkers), and the investigators are blinded to the treatment group.
- 3) With regard to potential financial interests of any investigators with pending patent applications at CU Anschutz, no such pending patent applications have been licensed and they have no current commercial value.
- 4) An independent **DSMB** has been established to oversee participant safety.
- 5) Notification of any financial interests of [name] or of other investigators in the study that may arise in the future will be made to the CU Research Compliance Office and appropriately managed, to editors of journals publishing study-related results and to the public in the context of communication of any research results.

- Appendix F: Common Terminology Criteria for Adverse Events (CTCAE) v5.0.
 - https://ctep.cancer.gov/protocoldevelopment/electronic_applications/docs/CTCAE_v5_Quick_Reference_5x7.pdf
- **Appendix G:** Evaluation of the safety and immunomodulatory effects of sargramostim in a randomized, double-blind phase 1 clinical Parkinson's disease trial (Gendelman et al., 2017).

Appendix H

General Rules for Excluded Concomitant Medications

This list is intended to be comprehensive, but not exhaustive. If a concomitant medication is in doubt, the decision of the Principal Investigator (PI), or Sponsor as specified, shall be the final determinant for allowance or not.

The PI will review all prior and concomitant medications, and review concomitant medication changes on an ongoing basis. If disallowed concomitant medications with exceptions for PRN use exceed frequencies as specified, the PI will be consulted prior to participant continuation in the study.

The PI and/or Sponsor may allow a participant to continue in the study while taking an excluded concomitant medication (or at an excluded frequency) on a case by case basis to ensure the safety of participants and the scientific validity of study data. Exceptions to excluded concomitant medications may be needed for situations such as treatment of an adverse event. Any exceptions to excluded concomitant medications or frequencies will result in a protocol deviation.

EXCLUDED CONCOMITANT MEDICATIONS1. Participation in any other investigational drug study within 4 weeks of screening (individuals may not participate in any other drug study while participating in this protocol).

- Any prior use of study drug that was investigated for anti-amyloid or anti-tauopothy effects, or AD vaccine, unless it can be documented that the participant was on placebo.
- Any prior use of sargramostim within 6 months of screening.
- 2. Diuretic drugs should not be started or discontinued within 4 weeks prior to screening. Any change in diuretic medication during the study should be reported.
- 3. As a class, chronic use of systemic corticosteroids are prohibited from within 4 weeks of screening through the follow-up visit due to possible risk of myeloproliferation.
- 4. Lithium is prohibited from within 4 weeks of screening through the follow-up visit due to possible risk of myeloproliferation.
- 5. Systemic immunosuppressive or immunomodulatory agents/drugs (other than corticosteroids, see below) are not permitted for a period of 60 days before screening. Rules for PRN use of select drugs that have a systemic effect, such as corticosteriods, are listed below.
- 6. Immunoglobulin therapy and biologic drugs are not permitted within 6 months before screening.
- 7. Off label or non-standard of care usage of leukotriene inhibitors, such as montelukast, are not allowed from before screening until after the final study visit.
- 8. AChEI and/or memantine therapy should follow standard of care parameters, and be a stable dosage for 60 days prior to and during screening. Initiation of, or changes to, AChEI or memantine therapy is strongly discouraged during the treatment period, and must be approved by the PI prior to change for participant continuation in the study. If changes occur without prior PI approval, the Sponsor must be consulted to approve of continuation in the study.
- 9. If a medication is found in more than one category, the rule for the most strict category will be used for use/exclusion.

ANTICOAGULATION THERAPY: Not allowed within 4 weeks prior to screening through follow-

up visit (with exception of 81 mg aspirin daily therapy)

GENERIC NAME	BRAND NAME	
Apixaban	Eliquis	
Dabigatran	Pradaxa	
Edoxaban	Savaysa	
Enoxaparin	Lovenox	
Fondaparinux	Arixtra	
Heparin		
Rivaroxaban	Xarelto	
Warfarin	Coumadin	

NARCOTIC ANALGESICS: Chronic use not allowed within 4 weeks prior to screening through follow-up visit PRN prescribed narcotic analgesic use is acceptable (Note definition of chronic use is weekly usage of a narcotic analgesic drug for three or more times per week AND for two or more weeks within any four-week period)

GENERIC NAME	BRAND NAME
Hydromorphone	Dilaudid
Oxycodone/Acetaminophen	Percocet
Oxycodone/Aspirin	Percodan
Propoxyphene/Darvon and its variations	
Narcotics that contain codeine or morphine	

NEUROLEPTICS: Not allowed within 4 weeks prior to screening through follow-up visit

GENERIC NAME	BRAND NAME
Chlorpromazine	Thorazine
Fluphenazine	Prolixin
Loxapine	Loxitane
Perphenazine	Etrafon, Trilafon
Thioridazine	Mellaril
Thiothixene	Navane
Trifluoperazine	Stelazine
Clozapine	Clozaril
Haloperidol	Haldol
Olanzapine	Zyprexa
Quetiapine	Seroquel

NEUROLEPTICS: Use of the following is permitted if dose is stable for 4 weeks prior to screening:

GENERIC NAME	BRAND NAME
Aripiprazole	Abilify
Risperidone	Risperdal (up to 2mg/day)
Ziprasidone	Geodon

ANTIPARKINSONIAN MEDICATIONS: Not allowed within 4 weeks prior of screening through follow-up visit

1010 11 415 1151	
GENERIC NAME	BRAND NAME
Amantadine	Symmetrel

Bromocriptine	Parlodel
Deprenyl/Selegilene	Eldepry
Levodopa	Sinemet
Pergolide	Permax
Pramipexole	Mirapex

SEDATIVES/BENZODIAZEPINES: Chronic use allowed if on stable doses 4 weeks prior to screening or PRN use if prescribed for a specific procedure.

GENERIC NAME	BRAND NAME
Alprazolam	Xanax
Buspirone	Buspar
Chloral Hydrate	Noctec
Chlordiazepoxide	Librium
Clonazepam	Klonopin
Diazepam	Valium
Flurazepam	Dalmane
Lorazepam	Ativan
Meprobamate	Miltown
Oxazepam	Serax
Temazepam	Restoril
Trazodone	Desyrel
Trizolam	Halcion
Zaleplon	Sonata
Zolpidem	Ambien

RHEUMATOID ARTHRITIS MEDICATIONS: Not allowed within 4 weeks of screening through follow-up visit

GENERIC NAME	BRAND NAME
Abatacept	Orencia
Adalimumab	Humira
Anakirna	Kineret
Barictinib	Olumiant
Betamethasone	Celestone
Certolizmab	Cimzia
Etanercept	Enbrel
Golimumab	Simponi
Hydroxychloroquine sulfate	Plaquenil
Infliximab-dyyb	Inflectra, Remicade
Leflunomide	Arava
Methotrexate	Rheumatrex/Trexall
Prednisone	
Rituximab	Rituxan
Sarilumab	Kevzara
Tocilizumab	Actemra
Tofacitinib	Xeljanz

ANTIHYPERTENSIVE AGENTS WITH FREQUENT CNS SIDE-EFFECTS: Not allowed within 4 weeks of screening through follow-up visit

Clonidine	Catapres

SYSTEMIC CORTICOSTEROIDS: Not allowed within 4 weeks of screening through follow-up visit excepting PRN or short course therapy as a necessary prescribed therapeutic for an acute condition. PI must be notified of use. (Note definition of chronic use is weekly usage of a systemic corticosteriod drug for three or more times per week AND for two or more weeks within any four-week period)

periou)	
GENERIC NAME	BRAND NAME
Cortisone	Cortone Acetate
Prednisone	Rayos, Sterapred, Deltasone
	Flo-Pred, Millipred, Orapred, Pediapred, Veripred
Prednisolone	20, Prelone, Hydeltra, Hydeltrsol, Key-Pred,
	Predacort, Predalone, Predate, Predaject,
	Medicort, Pri-Cortin, Predcor, AsmalPred
Methylprednisolone	Medrol, MethylPREDNIsolone
Dexamethasone	Baycadron, Decadron, Dexamethasone, Intensol,
	DexPak, TaperDex, Zema-Pak, ZoDex, Zonacort
Betamethasone	Celestone Soluspan, Pod-Care
hydrocortisone	Cortef

OTHER SYSTEMIC IMMUNOSUPPRESSANTS AND/OR IMMUNOMODULATORS NOT LISTED ELSEWHERE: Not allowed within 60 days of screening through follow-up visit.

GENERIC NAME	BRAND NAME
Cyclosporine	Neoral, Sandimmune, SangCya
Tacrolimus	Astagraf XL, Envarsus XR, Prograf
Sirolimus	Rapamune
Everolimus	Afinitor, Zortress
Azathioprine	Azasan, Imuran
Lefunomide	Avara
Mycophenolate	CellCept, Myfortic
Ixekizumab	Taltz
Natalizumab	Tysabi
Secukinumab	Consentyx
Ustekinumab	Stelara
Vedolizumab	Entyvio
Basiliximab	Simulect
Daclizumab	Zinbryta

